participant. This role will be referred to as ‘mixer’. Participants’ names are not disclosed to the mixer and the unblinded information will only be known to the randomizer. Is with knowledge of bag contents will be the designated mixer.

Blinding for Clinical Evaluators

To minimize assessment bias, clinical evaluators (data analysts and physicians) will be trained on how to maintain blinding to treatment as best as possible. “Best as possible” means that blinding will be maintained unless an adverse event occurs that requires unblinding the physician, which is determined by the medical monitor or DSMB. Training includes review of the process of blinding, describing who will be responsible for assigning product for the appropriate group, labels that will be used to identify subjects but not treatment group, and the process that should be followed if an adverse event occurs, triggering review by medical monitor and/or DSMB.

Planned Unblinding

Unblinding of patient information will only occur in the case of adverse event suspected to be related to the investigational product, per the medical monitor and DSMB.

Regulatory authorities and/or the IRB may request the unblinding of data from one or more patients at any time.

Investigational Product Assignment and Infusion Schedule (Staggering)

Each patient will be allocated a unique subject number at screening and will retain this number throughout the study.

The Investigational Product is to be administered to all eligible, enrolled patients in Arm 1.1 and Arm 2.1 by intravenous infusion at a dose of 1×10^8 cells at days 0, 3, 7, and 10. Every effort should be made to adhere to the dosing schedule. However, a scheduled infusion should not be administered if a patient has an ongoing AE that, in the Investigator’s opinion, warrants holding the infusion.

Prior and concomitant conditions

The investigators should document all prior significant medical history. Additional conditions present at the time when informed consent is given and up to the time of first infusion (Day 0) are to be regarded as concomitant conditions. Illnesses first occurring or detected during the study and/or worsening of a concomitant condition during the study should be documented as AEs in the CRF. The exception is that results from COVID-19 testing will be added to the CRF as part of medical history.

Prior and concomitant medications

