All medications, including over-the-counter treatments and preventative vaccines taken by the patient during the study, including those treatments initiated prior to the start of the study, must be recorded in the CRF. The entry must include the dose, regimen, route, indication, and dates of use.

Study Procedures

Table 2 outlines the timing of procedures, and assessments to be performed throughout the study.

Table 2. Schedule of Assessments

Visit Number	1	2	3	4	5	6
Days	N/A	Day 0	Day 3	Day 7	Day 10	Day 28
Visit Name	Screening	Baseline/ Infusion 1	Infusion 2	Infusion 3	Infusion 4	End of Study / Telephone Encounter**
Window Period	Up to 7 days	±3 days	±3 days	±3 days	±3 days	±3 days
STUDY PROCEDURES						
Informed Consent	X					
Demographics	X					
Inclusion and Exclusion Criteria	X					
Medical History Review	X	X	X	X	X	X
Concomitant Medication Review	X	X	X	X	X	X
Eligibility	X					
Randomization	X					
Adverse Event Monitoring		X	X	X	X	X
ASSESSMENTS						
Vital Signs	X	X	X	X	X	
Weight and Height ¹	X	X	X	X	X	
Physical Examination	X	X	X	X	X	
Ordinal Scale		X	X	X	X	X
CBC with differential	X	X	X	X	X	
Comprehensive Metabolic Panel	X	X	X	X	X	
Coagulation Panel	X	X	X	X	X	
Urinalysis with pregnancy test (childbearing age women only)	X					
PCR test for SARS-CoV-2		X	X	X	X	
Exploratory Laboratory Assessments ²		X	X	X	X	
Inflammatory Marker Laboratory Assessments ³		X	X	X	X	
EKG		X*	X*	X*	X*	
CT Scan		X				X
Chest X Ray (PA, Single View) ⁴		X				X
ADMINISTRATION						
Allogeneic HB-adMSCs Administration		X	X	X	X	

1. Height will only be measured at screening

2. Exploratory laboratory Assessments: Natural Killer Cell Surface Antigen (CD3-CD56+ Marker Analysis), Troponin, Myoglobin, Creatine Kinase (CK) MB, Serum ferritin, CD4+/CD8+ ratio, D-dimer

3. Inflammatory Marker Laboratory assessments: CRP, IL-6, IL-10, TNFa

4. Chest Xray and CT scan will be performed as scheduled, however, if the patient is discharged prior to the scheduled tests at 28 days, any imaging (CT/Xray) done at discharge

* Subsequent EKG will be performed if necessary, such as abnormal result at baseline

** Telephone encounter is conducted if subject has been discharged

Informed Consent (ICF)

Prior to commencement of any trial related activity, the investigator or designated staff will obtain written informed consent from the patient or their Legally Authorized Representative (LAR).

Patient Re-Screening

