- Medical History will be reviewed and updated if necessary. This includes recording results of COVID-19 testing. If the patient reported a medication which does not match the current medical history, further investigation will be required to determine whether it was an Adverse Event, or the patient just forgot to mention it before. If it is found to be an AE, it should be recorded in the appropriate CRF. If the patient forgot to mention it before, a note to file (NTF) should be made to clarify the case.
- A PCR analysis to detect SARS-CoV-2 virus will be performed with a nasal swab
- Blood samples will be collected for laboratory assessments.
- Ordinal Scale to be performed.
- Administer investigational product.
- Monitor for AEs. Observe the patient for at least 1 hour after infusion for symptoms of infusion-related reactions and allergic reactions, including anaphylaxis (See Appendix 1).
- Instruct the patient on recognition of delayed serious allergic reactions, including anaphylaxis and seeking for medical assistance.
- Chest X-ray will be performed or collected from hospitalization due to COVID-19.
- CT scan will be performed or collected from hospitalization due to COVID-19.

Infusion # 2 (Day 3) and #3 (Day 7) and #4 (Day 10)

- Weight will be measured
- Vital Signs will be measured.
- Concomitant medications will be reviewed and updated if necessary.
- Medical History will be reviewed and updated if necessary. This includes recording results of COVID-19 testing. If the patient reported a medication which does not match the current medical history, further investigation will be required to determine whether it was an Adverse Event, or the patient just forgot to mention it before. If it is found to be an AE, it should be recorded in the appropriate CRF. If the patient forgot to mention it before, a note to file (NTF) should be made to clarify the case.
- A PCR analysis to detect SARS-CoV-2 virus will be performed with a nasal swab
- Blood samples will be collected for laboratory assessments.
- Ordinal Scale to be performed.
- Administer investigational product.
- Monitor for AEs. Observe the patient for at least 1 hour after infusion for symptoms of infusion-related reactions and allergic reactions, including anaphylaxis (See Appendix 1).
- Instruct the patient on recognition of delayed serious allergic reactions, including anaphylaxis and seeking for medical assistance.

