The Investigator must review all laboratory reports and document the review. Any laboratory test result or change considered by the Investigator to be clinically significant should be considered an AE and recorded in the AE CRF. Clinically significant abnormal values occurring during the study will be followed until repeat test results return to normal, stabilize, or are no longer clinically significant.

Laboratory tests to be performed during the study:

Complete Blood Count with Differential	Natural Killer Cell Surface Antigen (CD3 ⁻ CD56 ⁺ Marker Analysis)
Complete Metabolic Profile	Il-10
Coagulation study (PTT/PT/INR)	CD4+ / CD8+ ratio
Urinalysis with pregnancy test	Creatine Kinase (CK)
C Reactive Protein	Troponin
Tumor Necrosis Factor alpha	Myoglobin (MB)
D-Dimer	VEGF
	Serum Ferritin

Adverse Events

An AE is any symptom, physical sign or disease that either emerges during the study or, if present at screening, worsens during the study, regardless of the suspected cause of the event. All medical and psychiatric conditions (except those related to the indication under study) present at screening will be documented in the medical history CRF. Changes in these conditions and new symptoms, physical signs, or diseases should be noted on the AE CRF during the rest of the study.

Clinically significant laboratory abnormalities should also be recorded as AEs. Surgical procedures that were planned before the patient enrolled in the study are not considered AEs if the conditions were known before study inclusion; the medical condition should be reported in the patient's medical history. Changes from baseline respiratory rate for non-ventilated subjects should also be considered as AE.

Serious Adverse Events (SAE)

A serious adverse event (SAE) is any AE that is:

- fatal
- life-threatening
- requires or prolongs hospital stay
- results in persistent or significant disability or incapacity
- Important Medical Events (IME): those events that may not result in death, be immediately life threatening, or require hospitalization. They may be considered a SAE when, based upon medical judgement, they may jeopardize the subject and may require intervention to prevent one of the other serious outcomes noted above. For example, drug overdose or abuse, a seizure that did not result in in-patient hospitalization, or intensive treatment of bronchospasm in an emergency department would typically be considered serious. (FDA, 21CFR312.32; ICH E2A and ICH E6)

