All SAEs must be reported to Hope Biosciences Stem Cell Research Foundation immediately after the Investigator becomes aware of the event, along with a determination as to whether it is associated with the study drug.

Patients will be instructed to report AEs at each study visit. All AEs are to be followed until resolution or until a stable clinical endpoint is reached.

Each AE is to be documented in the CRF with reference to onset date, duration, frequency, severity, relationship to study drug, treatment of event, and outcome. Furthermore, each AE is to be classified as being serious or non-serious. Changes in AEs and resolution dates are to be documented in the CRF.

For the purposes of this study, the period of observation for collection of AEs extends from the time the patient gives informed consent through day 28 (or early discontinuation visit). Follow-up of the AE is required until the event resolves or stabilizes at a level acceptable to the Investigator.

Intensity of Adverse Event

The intensity of the AE will be judged based on the following:

- Mild: Awareness of sign(s) or symptom(s) which is/are easily tolerated
- Moderate: Enough discomfort to cause interference with usual activity
- Severe: Incapacitating or causing inability to work or to perform usual activities

Causal Relationship of Adverse Events

Medical judgement will be used to determine the relationship, considering all relevant factors, including pattern of reaction, temporal relationship, de-challenge and confounding factors such as concomitant medication, concomitant disease and relevant history. Assessment of causal relationship will be recorded in the CRF.

- **Definitely Related:** The adverse event is clearly related to the investigational product – i.e. an event that follows a reasonable temporal sequence from administration of the study intervention, follows a known or expected response pattern to the suspected intervention, that is confirmed by improvement on stopping and reappearance of the event on repeated exposure and that could not be reasonably explained by the known characteristics of the subject's clinical state.
- **Possibly Related:** An adverse event that follows a reasonable temporal sequence from administration of the study intervention follows a known or expected response pattern to the suspected intervention, but that could readily have been produced by a number of other factors.

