#### **7.2.4.2. Data Analytic Models**

All secondary endpoint efficacy measurements available at post-baseline at scheduled measurements (Visits 2 through 5 [infusions 1 through 4] for exploratory markers and clinical labs; Visits 2 through 6 [infusion 1 through end of treatment] for chest X ray, CT scan, and ordinal scale score) will be analysed in a generalized linear mixed model. The model will predict each outcome as a function of the interaction between the fixed factors treatment group and time, controlling for lower order effects of time and treatment group. Models will control for stratification variables (see [Covariates and Other Strata](#)), and subject will be included as random effects. AEs/SAEs and AE severity will be analyzed as dichotomous outcomes (whether patient exhibited AE/SAE at any time during the study). AE/SAE attribution to study drug will be analyzed as count outcomes. All models will control for stratification variables.

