#### **8.1. Adverse Events Analyses**

AEs will be coded using the most recent version of the Medical Dictionary for Regulatory Activities (MedDRA).

A treatment emergent adverse event (TEAE) is defined as an event that has onset date on or after the first day of exposure to infusion treatment and no later than 3 days after the last day of infusion treatment. Here the first day of exposure is defined as the first day of exposure to infusion treatment.

Treatment Adverse events (TAES) are summarised descriptively, whereas non-TEAEs are presented in listings. TAE data will be displayed in terms of the number of subjects with at least one event (N), percentage of subjects with at least one event (%) and the number of events (E).

Summaries of TAEs and of serious AEs will be presented as an overview including all AEs, serious AEs, AEs by severity, AEs by relation to treatment, action to AEs and treatment advised, and outcome of AEs.

Furthermore, summary tables based on system organ class and preferred terms are made for:

- All TAEs
- Serious AEs
- AEs leading to withdrawal of study

Individual adverse events will be listed.

The details of the planned displays are in **Error! Reference source not found..**

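### The SAP's yes/no model of AE/SAE incidence has no onset rule, so events before the first infusion can count and would dilute the arm difference

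*SAP*

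**What the plan says.** - SAP 7.2.4.2 (Data Analytic Models, secondary endpoints) scores AEs/SAEs as dichotomous: "whether patient exhibited AE/SAE at any time during the study". It gives no start point and does not mention treatment emergence.
- The protocol, under Serious Adverse Events, says that "the period of observation for collection of AEs extends from the time the patient gives informed consent through day 28". Its general AE definition covers anything that "either emerges during the study or, if present at screening, worsens during the study", with no reference to infusion.
- The protocol, under Prior and concomitant conditions, says that conditions present at consent and "up to the time of first infusion (Day 0) are to be regarded as concomitant conditions".
- In Table 2 of the protocol, the row "Adverse Event Monitoring" is blank at Screening and marked from Day 0 to Day 28. The list of screening procedures has no AE step.
- The Day 0 procedures include a medical history review, listed before the product is given. If it turns up an unexplained medication, the instruction is: "If it is found to be an AE, it should be recorded in the appropriate CRF".
- SAP 8.1 defines a treatment-emergent event as "an event that has onset date on or after the first day of exposure to infusion treatment", ending 3 days after the last infusion day. Events outside that window go to listings only.

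**The concern.** The cumulative incidence of AEs or SAEs is a listed secondary endpoint, and SAP 7.2.4.2 is where the arms are compared on it by a model. If that model is programmed from the consent-to-Day-28 collection period, a patient with a new symptom during screening and nothing afterwards scores yes, although no product had been given. A patient with a pre-infusion AE also scores yes on the any-AE outcome whatever happens later.

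Such events cannot depend on arm, so they add the same expected background to both groups and pull the risk difference and odds ratio toward no difference. For a harm comparison that is the unsafe direction.

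The protocol's conflicting statements also mean that two sites could record the same screening-period event differently, one as an AE and one as medical history.

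**Working it through.** **Is there a plan figure to reproduce?** No. The protocol bases the sample size on anticipated demand and gives no AE rate, effect size or power. The only design figures are 100 patients at 3:2, which is 60:40.

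**Which texts let a pre-infusion event count?** The consent-to-Day-28 collection period, the general AE definition and the Day 0 history review do. The concomitant-conditions paragraph, Table 2 and the screening procedure list point the other way. SAP 8.1 keeps events dated before the first infusion day out of its treatment-emergent summaries, but 7.2.4.2 does not refer to it. No text says which rule governs the model.

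**Effect on the contrast.** Let q be the share of patients with a pre-infusion event, assumed equal in the arms and independent of later events. Let p be the post-infusion risk in an arm.

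- Any-time risk = q + (1 − q)p
- Any-time risk difference = (1 − q) × post-infusion risk difference

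**Plausible q.** Nobody is treated before infusion 1, so the untreated risk is the relevant one. Assume a 28-day untreated risk of 35% and a constant hazard, giving q = 1 − 0.65^(d/28) for d days from consent to infusion:

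- d = 1: 1.5%
- d = 3.5: 5.2%
- d = 7: 10.2%

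The 7-day limit is the protocol's screening period. SAP 2.2 gives 7 weeks instead, and that conflict is not used here.

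**Illustration.** Assume post-infusion risks of 60% (HB-adMSCs) and 35% (placebo), n = 60 and 40. Power uses the arcsine approximation at two-sided 5%: h = 2·arcsin√a − 2·arcsin√b, z = h × √(60 × 40/100) = 4.899h, power = Φ(z − 1.96), with a and b the any-time risks.

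| q | a | b | Difference | Odds ratio | h | z | Power |
|---|---|---|---|---|---|---|---|
| 0 | 60.0% | 35.0% | 25.0 points | 2.79 | 0.506 | 2.48 | 69.8% |
| 5% | 62.0% | 38.25% | 23.75 points | 2.63 | 0.480 | 2.35 | 65.2% |
| 10% | 64.0% | 41.5% | 22.5 points | 2.51 | 0.455 | 2.23 | 60.5% |

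**Limits.** The SAP's inference is Bayesian, with frequentist tests only supplementary (SAP 2.4), so power is a yardstick. The 60:40 split counts everyone randomised. SAP 7.2.3 puts secondary analyses by default on patients who received all four infusions, so the numbers analysed could be smaller. That is a separate matter.

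**The case against.** The best defence is that the problem may not arise. If sites follow the concomitant-conditions paragraph and Table 2, screening-period conditions go into medical history, q is about zero and the model is unaffected. The Day 0 list also places AE monitoring after administration of the product. A reader might infer from the collection-period sentence that pre-infusion events definitely count. The documents do not support that, only that they can.

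Other stronger readings also fail:

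- **That this is the only modelled safety comparison between arms.** SAP 7.2.4.2 also models AE severity, counts of events attributed to study drug, and clinical laboratories. The attribution count is largely protected, because the protocol's definitions of definitely and possibly related require a reasonable temporal sequence from administration.
- **That a pre-infusion event fixes all of a patient's safety scores.** SAEs are scored too, and a mild screening AE does not settle the SAE outcome.
- **That the loss could be much larger, say q = 20%.** With a 35% untreated risk and a constant hazard, even a full 7 days gives about 10%.
- **That worsening of a screening-period event would be lost because the original record keeps its onset date.** This depends on CRF conventions the documents do not describe. The protocol says worsening of a concomitant condition is to be documented as an AE.

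SAP 8.1 already limits its treatment-emergent summaries and sends other events to listings, so the descriptive safety tables are mostly sound on this point.

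What survives is that 7.2.4.2 has no onset rule and the protocol contradicts itself on when AE recording starts. A programmer therefore has no basis for choosing.

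**Conclusion.** The point holds in a limited form. The planned model of AE/SAE incidence can include events that precede any exposure, and any that are included shrink the risk difference by (1 − q). The direction is certain, given equal q in the arms and independence from later events. The size is unknown: the documents give neither an AE rate nor the actual time from consent to infusion, and q may be near zero.

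Under the stated assumptions the cost is modest, from about 1.5% of the risk difference with infusion a day after consent to about 10% if every patient spends the full 7 days in screening. In the illustration that largest case costs about 9 points of yardstick power (69.8% to 60.5%). The plan should be corrected because the ambiguity is avoidable and any bias makes a harmful product look safer.

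**What to change.** 1. In SAP 7.2.4.2, replace the any-time wording with: with onset, or worsening in severity or seriousness, after the start of the first infusion and through Day 28.
2. In SAP 8.1, use the start time of infusion 1 rather than the calendar day where onset time is recorded. As written, a Day 0 event that began before the infusion is treatment-emergent. Also add worsening after the first infusion, which the protocol's AE definition includes and 8.1 omits.
3. Do not import the 8.1 definition unchanged into 7.2.4.2. On schedule its window closes 3 days after Day 10, at Day 13, and would drop later events up to Day 28. Either state that the two windows differ on purpose or align them.
4. Reconcile the protocol's collection-period sentence with its concomitant-conditions paragraph and Table 2 on when AE recording starts.

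The cost is a few sentences and one derivation flag, with no new data. The downside is slightly fewer patients with an event in the model.

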### **8. SAFETY ANALYSES**

The safety analyses will be based on the Safety analysis set, unless otherwise specified.

#### **8.1. Adverse Events Analyses**

AEs will be coded using the most recent version of the Medical Dictionary for Regulatory Activities (MedDRA).

A treatment emergent adverse event (TEAE) is defined as an event that has onset date on or after the first day of exposure to infusion treatment and no later than 3 days after the last day of infusion treatment. Here the first day of exposure is defined as the first day of exposure to infusion treatment.

Treatment Adverse events (TAES) are summarised descriptively, whereas non-TEAEs are presented in listings. TAE data will be displayed in terms of the number of subjects with at least one event (N), percentage of subjects with at least one event (%) and the number of events (E).

Summaries of TAEs and of serious AEs will be presented as an overview including all AEs, serious AEs, AEs by severity, AEs by relation to treatment, action to AEs and treatment advised, and outcome of AEs.

Furthermore, summary tables based on system organ class and preferred terms are made for:

- All TAEs
- Serious AEs
- AEs leading to withdrawal of study

Individual adverse events will be listed.

The details of the planned displays are in **Error! Reference source not found..**

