## 4. ANALYSIS POPULATIONS

Population	Definition / Criteria	Analyses Evaluated
Safety analysis set	

• All randomised subjects who received at least one dose of HB-adMSCs infusion or placebo.

• If participants receive a treatment different to their randomized treatment, they will be analysed according to the treatment actually received.

	

• Safety

• Study Population

Efficacy analysis set	

• All randomized participants who received all 4 infusions of HB-adMSCs or placebo.

• Participants will be analysed according to their randomized treatment.

	

• Efficacy

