The Bayesian approach addresses these questions: (1) “Among patients with suspected COVID-19, what is the probability that allogeneic HB-adMSC 100mm confers benefit relative to placebo on status on inflammatory markers (C-Reactive protein, TNF-alpha, IL-6, IL-10), change from baseline oxygenation, and time to return to room air (RTRA) at treatment Day 10?” (2) “What is the best estimate of these effects?” and (3) “What is their precision?” By estimating the probability that such effects exist, we are assessing the probability that the alternative hypothesis is true; a probability that is, by definition, not accessible to Frequentist methods. The FDA has discussed the use of Bayesian statistical methods to make decisions regarding the efficacy of new treatments as an alternative to Frequentist methods in developing clinical applications. The current proposal will provide the optimal, unbiased estimates for the benefit conferred by allogeneic HB-adMSC, while also estimating the probability that such effects exist. Posterior distributions can then be used as informative priors for continued monitoring in expansions of treatments and treatment strategies exhibiting initial promise.

Presentation of results from the statistical models will include the estimated conditional/marginal mean treatment effects. For all endpoints analysed statistically, estimated mean treatment differences will be presented together with 95% credible intervals and posterior probabilities,

HB-adMSCs 100MM vs Placebo

All safety evaluations will be presented using Safety Analysis Set. The efficacy analysis will be presented using Efficacy analysis set.

Individual safety and efficacy parameters will be listed.

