## 7.2. Secondary Efficacy Analyses

### 7.2.1. Endpoints / Variables

Change from baseline through Visit 5 (Day 10):

- Change in clinical laboratories
- Change from baseline in exploratory markers (D-dimer, myoglobin, troponin, creatinine kinase, serum ferritin, CD3CD56, CD4/CD8, VEGF)

Change from baseline through Visit 6 (Day 28):

- Change from baseline Chest X-ray (available at Visit 6 only)
- Change from baseline CT scan (available at Visit 6 only)
- Time to negative PCR test results
- Change from baseline in the 7-point ordinal scale

Cumulative:

- Cumulative incidence of serious adverse events (SAEs) or adverse events (AEs)

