### 7.2.3. Population of Interest

The secondary efficacy analyses will be based on the Efficacy analysis set population, unless otherwise specified.

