### 7.2.4.1. Statistical Methodology Specification

Principles will follow the same procedures as the Primary Efficacy analyses (see 7.1.4.1). Three sets of analyses will be performed: the first adjusting for stratification variables, a second set adjusting for variables found to be confounding (see 7.1.4.1), and a third set focusing on the subgroup of surviving patients as of the last infusion where statistically feasible. Bayesian generalized multilevel models will evaluate the differential trajectories of each secondary endpoint as a function of treatment, time, and the interaction of treatment and time.

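### The treatment-emergent AE tables stop 3 days after the last infusion although AEs are collected to Day 28, and the whole-study AE/SAE analysis names no population

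*SAP*

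**What the plan says.** **The tables.** SAP 8.1 starts the treatment-emergent window on the first infusion day and ends it "no later than 3 days after the last day of infusion treatment". It continues: "Treatment Adverse events (TAES) are summarised descriptively, whereas non-TEAEs are presented in listings". Organ-class and preferred-term tables are planned for all TAEs, for serious AEs and for AEs leading to withdrawal. The last two state no window. The cross-reference to the planned displays does not resolve, so it cannot clarify the periods.

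**The data collected.** The protocol (Serious Adverse Events) collects AEs from consent to Day 28 or the early discontinuation visit. Its withdrawal section keeps patients who stop infusions, with consent, in follow-up to Day 28. Its Endpoints section makes AE and SAE incidence a primary safety endpoint; SAP 2.1 and 7.2.1 list it as a secondary endpoint.

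**The whole-study analysis.** SAP 7.2.2 promises unadjusted and model-based summaries for every secondary endpoint. SAP 7.2.4.2 adds: "AEs/SAEs and AE severity will be analyzed as dichotomous outcomes (whether patient exhibited AE/SAE at any time during the study". It names no population.

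**The population rules.** SAP 7.2.3: "The secondary efficacy analyses will be based on the Efficacy analysis set population, unless otherwise specified". SAP 4 defines that set as: "All randomized participants who received all 4 infusions of HB-adMSCs or placebo". Against this, SAP 5.7 says: "All safety evaluations will be presented using Safety Analysis Set". SAP 4 and SAP 8 also tie safety to the Safety set (at least one infusion).

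Two readings are mine. TAE is not defined, and I take it as TEAE. SAP 8.1 does not say that its tables are split by arm; I infer this from the treatment descriptors in SAP 5.2.

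**The concern.** There are two separate issues.

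First, the length of follow-up behind the main AE table is set by something that happens after randomization, namely when the patient was last infused. The protocol allows a scheduled infusion to be withheld for an ongoing AE. Poor tolerability can therefore shorten the time over which a patient's AEs are tabulated, if no later infusion is given. Crude percentages by arm would then rest on unequal follow-up, and the type of any late non-serious AE would be visible only in a listing, which gives no incidence.

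Second, if the AE/SAE model used the Efficacy set, it would leave out everyone who stopped or died before the fourth infusion. Those are patients in whom a safety comparison matters most. Late non-serious AEs in patients who stopped but stayed in follow-up could then be in neither the tables nor the model.

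**Working it through.** The plan gives no figure to reproduce, so this is day arithmetic followed by a comparison of the population rules.

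**Inputs.** Infusions are on Days 0, 3, 7 and 10 (Protocol, infusion schedule; SAP 2.2). The end of study is Day 28, and visits have a window of ±3 days (Protocol, Table 2). Two statements do not fit this schedule and must be reconciled with it: SAP 2.2 also gives a treatment duration of up to 7 days, and the protocol's DSMB section puts one group's third infusion on day 14. I used the four listed dates.

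**Coverage.** Window end = last infusion day + 3. Days covered = window end + 1. Days outside = 28 − window end. Days 0 to 28 make 29 days. Scheduled AE-monitoring visits in Table 2 are Days 0, 3, 7, 10 and 28.

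| Last infusion | Window ends | Days covered | Days outside (of 29) | AE visits outside (of 5) |
|---|---|---|---|---|
| Day 10 | Day 13 | 14 | 15 (52%) | 1 (Day 28) |
| Day 7 | Day 10 | 11 | 18 (62%) | 1 (Day 28) |
| Day 3 | Day 6 | 7 | 22 (76%) | 3 (Days 7, 10, 28) |
| Day 0 | Day 3 | 4 | 25 (86%) | 3 (Days 7, 10, 28) |

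With the visit windows, the Day 10 row ranges from 25 − (13 + 3) = 9 days outside to 31 − (7 + 3) = 21.

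These are shares of time, not of events. No visit is scheduled between Day 10 and Day 28, and Day 28 is a telephone contact for discharged patients, so the visit count is the fairer guide.

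**Events that end treatment.** After infusions on Days 0, 3 and 7 the window ends on Days 3, 6 and 10; the next infusions are due on Days 3, 7 and 10. An AE that starts by the day of the next infusion and leads to its being withheld is therefore inside the window. The one exception is onset on Day 7 after a last infusion on Day 3, which falls one day outside if no further infusion is given.

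**Which by-arm display a non-serious AE reaches** (leaving aside AEs that lead to withdrawal):

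| Event | If SAP 7.2 uses the Safety set | If SAP 7.2 uses the Efficacy set |
|---|---|---|
| Inside window | Term table, summary and model | Term table; summary and model only after four infusions |
| After window, four infusions given | Summary and model only | Summary and model only |
| After window, fewer than four given | Summary and model only | None; listing only |

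The model records whether a patient had any AE, so it does not show which kinds of late event occurred.

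**How many patients the population choice could move.** The protocol assumes 15% drop-out: 0.15 × 100 = 15 patients, or 0.15 × 60 = 9 and 0.15 × 40 = 6 by arm, leaving 85 (51 and 34). This assumes that every drop-out had at least one infusion but not all four. If all drop-outs came after the fourth infusion, the loss from this source would be 0. Patients who missed an infusion without dropping out would add to it.

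**The case against.** The strongest reply has four parts.

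- **The population is close to settled.** The default in 7.2.3 yields to anything specified elsewhere, and SAP 5.7 assigns all safety evaluations to the Safety set without qualification. The planned survivor analysis, "a third set focusing on the subgroup of surviving patients as of the last infusion where statistically feasible", would be nearly redundant among four-infusion recipients and so also hints at a wider set, though it is generic wording for all secondary endpoints. I accept that the Safety set is the more natural reading. What stands is that 7.2.4.2 sits under the 7.2.3 default, names no set, and should not need interpretation.
- **A whole-study summary already exists.** A reader might infer that late AEs enter no comparison between arms. SAP 7.2.1, 7.2.2 and 7.2.4.2 do not support that: overall incidence is planned both descriptively and by model. The gap that remains on the Safety-set reading is the breakdown of late non-serious AEs by organ class and term.
- **No event is lost.** Individual AEs are all listed. The protocol's Safety Analysis section asks only that AEs and SAEs be recorded and reported, without asking for a split by arm, so no breach is shown. The SAE and withdrawal tables state no window and may already run to Day 28. The overview in 8.1 mentions all AEs, although it is introduced as a summary of TAEs and serious AEs.
- **An exposure-linked window is a legitimate choice.** That is so, and it can stay as a subset table.

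It would also be wrong to read the window as shrinking with the number of infusions. It follows the date of the last one: a patient infused on Days 0, 3 and 10 has had three infusions and still has the full 14 days.

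**Conclusion.** The point holds as a reporting gap with an inexpensive remedy. As written, the organ-class and preferred-term table of AEs omits non-serious events that start more than 3 days after the last infusion, although they are collected. It covers 14 of 29 nominal days for a patient last infused on Day 10, and 11, 7 or 4 for one last infused on Day 7, 3 or 0. The shorter figures need a patient who stops for good and remains in follow-up; the documents do not say how many there will be. For patients who withdraw, AE collection ends at the early discontinuation visit, so the 29-day denominator does not apply to them.

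The exclusion of early stoppers from the AE/SAE model is conditional on the less natural reading of the population rules.

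A reader might infer that the tables favour one arm. The documents do not show that stopping differs by arm, nor how late events are distributed, so neither the direction nor the size of a bias can be derived. The conclusion rests on reading TAE as TEAE and on the tables being split by arm.

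**What to change.** 1. In SAP 7.2.3 or 7.2.4.2, state that the AE/SAE summaries and models use the Safety analysis set, with onset through Day 28 or last contact.
2. Add by-arm organ-class and preferred-term tables of all AEs from first infusion through Day 28 or last contact, for every dosed patient whatever the number of infusions.
3. Keep the 3-day treatment-emergent table as a subset.
4. State that the serious-AE and withdrawal tables are not limited to that window.
5. Define TAE or replace it with TEAE, and say that the tables are presented by arm.

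The cost is some SAP wording and a few tables from data already collected; the SAP copy reviewed is marked as a draft. The price in interpretation is more background COVID-19 events in both arms, which is a reason to retain the subset table alongside.
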